## 9. SAFETY REPORTING

### 9.1 Section 10 WMO event

In accordance to section 10, subsection 1, of the WMO, the investigator will inform the subjects and the reviewing accredited METC if anything occurs, on the basis of which it appears that the disadvantages of participation may be significantly greater than was foreseen in the research proposal. The study will be suspended pending further review by the accredited METC, except insofar as suspension would jeopardise the subjects' health. The investigator will take care that all subjects are kept informed.

### 9.2 AEs, SAEs and SUSARs

#### 9.2.1 Adverse events (AEs)

Adverse events are defined as any undesirable experience occurring to a subject during the study, whether or not considered related to one of the two approaches for hip arthroplasty. All adverse events reported spontaneously by the subject or observed by the investigator or his staff will be recorded.

#### 9.2.2 Serious adverse events (SAEs)

A serious adverse event is any untoward medical occurrence or effect that at any dose:

- results in death;
- is life threatening (at the time of the event);
- requires hospitalisation or prolongation of existing inpatients' hospitalisation;
- results in persistent or significant disability or incapacity;
- is a congenital anomaly or birth defect;
- Any other important medical event that may not result in death, be life threatening, or require hospitalization, may be considered a serious adverse experience when, based upon appropriate medical judgement, the event may jeopardise the subject or may require an intervention to prevent one of the outcomes listed above.

The sponsor will report the SAEs through the web portal *ToetsingOnline* to the accredited METC that approved the protocol, within 15 days after the sponsor has first knowledge of the serious adverse events. SAEs that result in death or are life threatening should be reported expedited. The expedited reporting will occur not later than 7 days after the responsible investigator has first knowledge of the adverse reaction. This is for a preliminary report with another 8 days for completion of the report.

If prolongation of hospital stay is due to logistical reasons (e.g. a patient is placed on a waiting list for a place in a rehabilitation centre), it will not be reported as an SAE. Prolongation of hospital stay or re-hospitalizations due to infection or luxation of the hip prosthesis are considered a standard risk in THA. In addition, a retrospective analysis in the Medical Centre Alkmaar (see introduction section) showed no differences in the occurrence of these events between DAA and PLA. Therefore they will not be reported as an SAE.

**9.2.3 Suspected unexpected serious adverse reactions (SUSARs)**

Not applicable

**9.3 Annual safety report**

Not applicable

**9.4 Follow-up of adverse events**

All AEs will be followed until they have abated, or until a stable situation has been reached.

Depending on the event, follow up may require additional tests or medical procedures as indicated, and/or referral to the general physician or a medical specialist.

SAEs need to be reported till end of study within the Netherlands, as defined in the protocol

**9.5 [Data Safety Monitoring Board (DSMB) / Safety Committee]**

A DSMB was not deemed necessary for this study as the treatment is non-critical and does not carry substantial additional risks as stated above.

## 10. STATISTICAL ANALYSIS

The intention to treat (ITT) population consists of all patients that are assigned randomized irrespective of being treated according to the protocol but at least underwent a THA. The per-protocol (PP) population comprises those patients of the ITT population who underwent a THA according to treatment allocation and have a score on the primary outcome variable.

### 10.1 Primary study parameter(s)

Continuous study parameters are described in terms of means and standard deviations if the data are normally distributed. If the data are not normally distributed then they are described in terms of median, interquartile range and minimum and maximum values. Categorical study parameters are described as proportions.

It shall be investigated if THA using DAA leads to better values of the (primary) clinical outcome parameters postoperatively and at follow-up compared to THA using PLA. In case parametric assumptions are not violated, standard parametric statistical methods will be applied (GLM (General Linear Model)), otherwise non-parametric methods will be used. The same procedure is performed for differences in changes in the primary study parameters at follow-up compared to preoperative values within one patient. Categorical outcome parameters will be analysed using Chi-square tests. If possible, 95% confidence intervals for the relevant estimates will be calculated. In addition to the univariate analyses, the longitudinal differences (effects of time) in the primary study parameters between the participants that received a THA using the DAA or PLA will be analysed in multiple regression models using random coefficient analyses. In these analyses the longitudinal differences between the two surgical procedures is studied accounting for the participation of three surgeons and possible confounding and effect modification of other determinants of the outcome parameters. The random coefficient analyses account for the dependency of the repeated measurements of the longitudinal study.

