#### 4.4 Sample size calculation

The primary outcome is the clinical outcome. As we expect faster recovery for the DAA compared to the PLA, but an equal outcome in the long term, we want to detect a significant difference at 3 months. We calculated the sample size using the Hip Dysfunction and Osteoarthritis Outcome Score (HOOS) and the VAS score for perceived pain. Both these measurements are included in the Patient Related Outcome Measures (PROMs), which are currently the nationwide standard for the evaluation of orthopaedic treatments in the Netherlands used by hospitals and insurance companies.

The HOOS is a disease specific measure assessing pain and function of the hip in 5 different subscales (symptoms, pain, activities of daily living (ADL), sports & recreation, quality of life). In each subscale patients can score up to 100 points, with 0 points being the worst score and 100 points the best. To detect a clinically relevant difference of 7 points in the HOOS symptoms, pain or ADL subscales and using a standard deviation (SD) of 15 points with a two-sided 5% significance level and a power of 80%, a sample size of 72 patients per group is necessary. To detect a difference in VAS score (0-10) of 1 point, i.e. a score of 2.5 SD 2 for the PLA and 1.5 SD 2 for the DAA with a two-sided 5% significance level and a power of 80%, a sample size of 64 patients per group is necessary. Given an anticipated dropout rate of 20% during the 2-year follow-up, we will recruit 2 times 86 patients, 172 patients in total.

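### Section 10.1 sets two unranked analyses (value and change) and a data-dependent choice of test for each primary score; one baseline- and surgeon-adjusted 3-month contrast would be clearer and at least as precise

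*Protocol*

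**What the plan says.** Protocol section 8.1.1 defines four primary variables, all at three months: the HOOS symptoms, pain and ADL subscales and the VAS for pain. Section 4.4 sizes the trial for a 3-month difference, using a "clinically relevant difference of 7 points in the HOOS symptoms, pain or ADL subscales" and, for the VAS, "a score of 2.5 SD 2 for the PLA and 1.5 SD 2 for the DAA".

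Section 10.1, on the primary parameters, sets out:

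- a comparison of the scores between approaches after surgery and at follow-up, with no month named;
- a second comparison: "The same procedure is performed for differences in changes in the primary study parameters at follow-up compared to preoperative values within one patient";
- for both, a choice of method that depends on the data: "In case parametric assumptions are not violated, standard parametric statistical methods will be applied (GLM (General Linear Model)), otherwise non-parametric methods will be used";
- in addition to these analyses, which it calls univariate, random coefficient models over time that allow for the three surgeons and for "possible confounding and effect modification of other determinants of the outcome parameters".

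Baseline HOOS and VAS are collected (section 8.3, Table 1). In 10.1 the baseline score is used only by subtraction and is not named as a covariate. Surgeon is named only in the additional longitudinal model.

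**The concern.** A reader of 10.1 cannot tell which result answers the primary question for a given score. The 3-month value and the change to 3 months can give different p-values, and each can come from either of two families of test. This leaves room to emphasise the more favourable result and raises the false-positive chance if either is allowed to count.

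The switch of test also affects what is estimated. A general linear model estimates a mean difference, which is the quantity in section 4.4. The usual rank test does not. Two primary scores could therefore end up with different effect measures, chosen after the data are seen.

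Finally, a pre-operative measurement of every primary score is available, and neither planned univariate analysis makes the most efficient use of it.

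**Working it through.** **Inputs from section 4.4.** HOOS: difference 7, "using a standard deviation (SD) of 15 points", two-sided 5%, 80% power, 72 per group. VAS: means 2.5 and 1.5, SD 2, 64 per group. Recruitment: "Given an anticipated dropout rate of 20% during the 2-year follow-up, we will recruit 2 times 86 patients, 172 patients in total".

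**Assumptions not in the protocol.** The correlation r between the baseline and 3-month score is varied over 0.2, 0.3, 0.5 and 0.7. The SD is taken as equal at both times.

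**1. The plan's own figures.** n per group = 2 × [SD × (1.96 + 0.8416) / difference]².

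- HOOS: 2 × (15 × 2.8016 / 7)² = 72.08; the plan states 72.
- VAS: 2 × (2 × 2.8016 / 1)² = 62.79; the plan states 64, and the t-test version gives 63.77.

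Both fit an unadjusted comparison of raw 3-month scores.

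**2. Power of the three analyses.** Evaluable per arm: 86 × 0.8 = 68.8. Power = Φ(7 / [SD_eff × √(2/68.8)] − 1.96), where SD_eff is:

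- raw 3-month value: 15;
- change score: 15 × √(2(1 − r));
- baseline-adjusted (ANCOVA): 15 × √(1 − r²).

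| r | Raw value | Change score | Baseline-adjusted |
|---|---|---|---|
| 0.2 | 78.1% | 58.1% | 79.8% |
| 0.3 | 78.1% | 63.8% | 81.8% |
| 0.5 | 78.1% | 78.1% | 88.5% |
| 0.7 | 78.1% | 94.2% | 96.9% |

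Worked example, r = 0.5, adjusted: SD_eff = 15 × √0.75 = 12.99; 7 / (12.99 × √(2/68.8)) = 3.16; Φ(3.16 − 1.96) = 88.5%. Power from the t distribution is lower by 0.6 of a percentage point or less.

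The ordering is general. 1 − r² never exceeds 1, and it never exceeds 2(1 − r), because 2(1 − r) − (1 − r²) = (1 − r)². The change score is weaker than the raw value below r = 0.5 and stronger above it.

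**3. False positives from testing both value and change.** Simulated with normal data, 69 per arm, no true effect and each test at 5%, counting a success if either is significant. The chance of a false positive for one endpoint is about 8.4% to 9.4% over r = 0.2 to 0.7. This leaves out the switch of test, the other time points, the longitudinal model and the presence of four primary variables.

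**4. VAS and the switch.** The scale runs from 0 to 10. A normal variable with mean 1.5 and SD 2 would have Φ((0 − 1.5)/2) = Φ(−0.75) = 22.7% of its values below zero. With mean 2.5 the share is Φ(−1.25) = 10.6%. On the protocol's own figures, the 3-month VAS cannot be close to normal.

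**The case against.** Much can be said for the plan, and several stronger readings fail.

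- **No time point.** Sections 4.4 and 8.1.1 fix 3 months, and 10.1 refers to the primary parameters they define. The time point exists; 10.1 only fails to carry it over.
- **Three rival primary results.** A reader might count the random coefficient model as a third. Section 10.1 introduces it as additional to the univariate analyses, so the ambiguity lies between value and change.
- **A straight-line model that dilutes an early benefit.** Section 10.1 does not say that time enters linearly, so this cannot be inferred.
- **Confounders picked from the data.** The text speaks of possible confounding and states no selection rule.
- **The planned test loses power.** Against the plan's own basis the raw comparison loses nothing, because section 4.4 was built on it. The 78.1% rather than 80% comes from the dropout allowance (72 × 1.2 = 86.4, whereas 72 / 0.8 = 90), which is a separate matter. Under randomisation, the mean contrasts from the raw, change and adjusted analyses all estimate the same difference, so adjustment improves efficiency and does not repair an invalid test.
- **VAS will go to a rank test.** Section 10.1 gives no criterion for a violated assumption, so this is possible but not certain.
- **No covariates.** That the comparisons are unadjusted is inferred from the word univariate. A general linear model can hold covariates, but none is named for it.

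A statistical analysis plan could choose one model and list covariates. The point that stands is what 10.1 itself fixes: two unranked analyses per score and a choice of test that depends on the data.

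**Conclusion.** The point holds in this limited form and should be fixed before the data are analysed. The planned raw comparison is valid; the weakness is that it is not singled out, its method can change with the data, and a more precise analysis is available without extra data.

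The false-positive chance is roughly 8-9% per endpoint, provided a significant result on either value or change would be taken as success. The protocol neither says so nor excludes it. The gain from baseline adjustment over raw values is under 2 percentage points of power at r = 0.2, about 4 at 0.3, 10 at 0.5 and 19 at 0.7. The correlation is assumed throughout, so the direction is certain and the size is not. The gain from surgeon adjustment cannot be computed from the protocol.

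**What to change.** In section 10.1, name one primary analysis for each of the four scores: a linear model of the 3-month value on treatment arm, the baseline value of the same score, and surgeon (three levels). Report the adjusted mean difference with a robust or bootstrap 95% confidence interval, whatever the distribution looks like, so that no check of assumptions changes the effect measure. Label the raw-value, change-score, rank-based and random coefficient analyses as supportive.

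The cost is a rewording of 10.1. Baseline scores are already collected and surgeon is already used in the longitudinal model, so no patient, visit or measurement is added. The interval method must be written in for the clinical scores, since the bootstrapping in section 10.2 covers only costs and the cost-effectiveness and cost-utility ratios.

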### 10.2 Secondary study parameter(s)

The secondary study parameters (functional and surgical parameters) are to be analysed in the same manner as the primary study parameters.

In addition the cost effectiveness analysis (CEA) will be performed alongside the trial from a societal perspective. We will compare the differences in total costs between DAA and PLA to difference in effect (pain/VAS and symptoms/HOOS). We will also perform a cost-utility analysis based on the EQ-5D using Dutch tariffs. All relevant costs of the interventions, other direct medical costs (e.g. rehabilitation and medication) and productivity losses are assessed using cost-questionnaires at 0, 3, 6, 9 and 12 months after surgery. Bootstrapping will be used for pair-wise comparison of the mean differences in total costs. Cost-effectiveness and cost-utility ratios will be estimated using bootstrapping techniques and graphically presented on cost-effectiveness and cost-utility planes. Acceptability curves will also be presented.

A budget impact analysis will be conducted according to the ISPOR international guidelines and from different perspectives (health care, society). Available Dutch epidemiological data will be used to estimate the incidence and prevalence. The current and future mix of interventions

(different implementation levels) will be used to estimate long-term financial consequences. Costs will be estimated using tariffs from the Dutch Care Authority. Different scenarios using different care and population mixes will be modelled and sensitivity analyses performed.

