### 8.3 Study procedures

#### *Pre-operative assessment*

After inclusion participants will be asked to fill in a questionnaire. A general questionnaire containing questions about demographic characteristics of the participants, and validated questionnaires to assess clinical and functional outcomes and cost-effectiveness will be used. The Hip Dysfunction and Osteoarthritis Outcome Score (HOOS) will be used to assess pain, symptoms and function of the hip in relation to different activities of daily life. Also, a Visual Analogue Scale (VAS) will be used to assess perceived pain in the previous week. To assess quality of life, the participant will be asked to fill in the EQ-5D. A part of the questionnaire will be dedicated to questions concerning the financial costs associated with the hip problems of the participants to assess the cost-effectiveness of the approaches for hip arthroplasty. This part of the questionnaire is generally applied in cost-effectiveness studies and at some points specifically adjusted to hip problems.

In addition to the self-reported HOOS, the quality of movement and walking will be quantified to assess functional outcome. Basic balance and gait performance will be tested using the timed "up & go" (TUG) test, instrumented with inertial sensors to measure trunk accelerations, and a two times 50 meter walk at their preferred walking speed, also instrumented with inertial sensors. For the TUG test, in short, participants will be asked to stand up from a chair, walk for 3 meters, walk back to the chair and sit down on the chair. The time needed to perform the TUG as instructed will be registered. In addition, the participants will wear inertial sensors (McRoberts Dynaport Hybrid, Dimensions 87 x 45 x 14 mm, Weight 74 grams), which will be attached to the trunk using a comfortable elastic belt with Velcro fixation. The inertial sensors measure the accelerations of the trunk. Pre-operatively, standard radiographs of the pelvis (anterior posterior or AP and lateral views) are performed.

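### Section 10.2 names no baseline adjustment for the economic comparison, although pre-operative EQ-5D and month-0 costs are collected and could be used as covariates at almost no cost

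*Protocol*

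**What the plan says.** Section 10.2 sets out the economic evaluation separately from the other secondary analyses.

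- **Utility.** "We will also perform a cost-utility analysis based on the EQ-5D using Dutch tariffs". No QALY formula, comparison model or covariate follows.
- **Costs.** "Bootstrapping will be used for pair-wise comparison of the mean differences in total costs".
- **Ratios.** "Cost-effectiveness and cost-utility ratios will be estimated using bootstrapping techniques and graphically presented on cost-effectiveness and cost-utility planes". Acceptability curves are added.
- **Timing of cost data.** Costs are taken from "cost-questionnaires at 0, 3, 6, 9 and 12 months after surgery".

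Baseline values are available. For the pre-operative assessment, section 8.3 says: "To assess quality of life, the participant will be asked to fill in the EQ-5D". The same questionnaire has a cost part. Table 1 schedules EQ-5D pre-operatively, at 6 weeks and at 3, 6, 12 and 24 months, and the economic parameters pre-operatively and at 3, 6, 9 and 12 months. Section 8.2 places the baseline measurements before allocation.

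The clinical analyses do use baseline. Section 10.1 says: "The same procedure is performed for differences in changes in the primary study parameters at follow-up compared to preoperative values within one patient". It adds random coefficient models that account for surgeon and possible confounders. Section 10.2 carries this over as follows: "The secondary study parameters (functional and surgical parameters) are to be analysed in the same manner as the primary study parameters". The bracket does not mention the economic parameters.

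**The concern.** The protocol uses pre-operative values for its clinical outcomes and names a method without them for costs. If QALYs are also compared as a difference in arm means, two things follow.

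First, a chance difference in utility before surgery enters the QALY difference. It does so directly if baseline is the first point of an area under the curve, and indirectly because patients who start better tend to score better later. Section 8.2 describes 1:1 allocation in blocks of 10 and states no stratification that would limit such imbalance. Second, the part of the between-patient variance that baseline explains stays in the standard error.

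Cost-effectiveness is a secondary objective. Section 4.4 expects faster recovery but an equal long-term outcome, so any QALY gain is likely to be short-lived. A small effect is the situation in which imbalance and lost precision matter most for the planes and acceptability curves.

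The role of the month-0 costs is also left open. Section 10.2 lists that questionnaire with the others under a phrase about time after surgery, whereas section 8.3 and Table 1 place it before surgery. Costs incurred before allocation cannot be caused by the approach.

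**Working it through.** **The plan's own figures.** The economic analysis has no stated sample size, SD or expected difference. The nearest figure is the HOOS sample size in section 4.4 (difference 7, SD 15, two-sided 5%, power 80%): n = 2 × [15 × (1.960 + 0.842) / 7]² = 72.1 per group, against 72 stated. The protocol recruits 86 per group and anticipates 20% dropout, so 86 × 0.8 = 68.8, about 69 completers per arm. That dropout is stated for two years and the cost data end at 12 months, so the number may lie between 69 and 86. The percentages in step 1 do not depend on it.

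**Assumptions, none from the documents.** Baseline-outcome correlation 0.3 to 0.5 in step 1. Baseline EQ-5D SD 0.20 to 0.30 in step 2. In step 3, baseline SD 0.25, follow-up SD 0.20, correlation between follow-ups 0.6 and baseline/follow-up correlation 0.1 to 0.5.

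**Step 1: precision.** Adjusting for a baseline with correlation ρ to the outcome multiplies the variance by 1 − ρ².

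| ρ | 1 − ρ² | Reduction in SE, 1 − √(1 − ρ²) | Equivalent n per arm, 69/(1 − ρ²) |
|---|---|---|---|
| 0.3 | 0.91 | 4.6% | 75.8 |
| 0.4 | 0.84 | 8.3% | 82.1 |
| 0.5 | 0.75 | 13.4% | 92.0 |

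**Step 2: direct share of baseline.** This step and the next suppose that QALYs are formed by the trapezoid rule over 0, 6 weeks, 3, 6 and 12 months; the protocol does not say so. Baseline then has weight 0.5 × 6/52 = 0.0577. The SE of the baseline difference is SD × √(2/69): 0.034 for SD 0.20 and 0.051 for SD 0.30. A 1.96-SE imbalance is 0.067 to 0.100 utility. Multiplied by 0.0577, it moves the QALY difference by 0.004 to 0.006.

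**Step 3: including carry-over to later scores.** The slope of QALY on baseline is 0.0577 + ρ × (0.20/0.25) × (1 − 0.0577).

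- ρ = 0.1: slope 0.133. A 1.96-SE imbalance is 1.96 × 0.25 × √(2/69) = 0.083, so the shift is 0.011 QALY. The SE of the QALY difference falls from 0.0275 to 0.0269 with adjustment.
- ρ = 0.5: slope 0.435, shift 0.036 QALY. The SE falls from 0.0287 to 0.0219.

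The implied correlation between QALY and baseline is 0.21 and 0.65 respectively.

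**Step 4: costs.** No cost SD or correlation is given, so nothing can be computed.

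**The case against.** The strongest reply is that much of this rests on silence. A reader might infer that the protocol fixes an unadjusted comparison of QALYs. It does not: the mean-difference sentence covers total costs only, no QALY formula is given, and bootstrapping describes how uncertainty is obtained and works equally well around a regression. Baseline adjustment is also detail that is commonly left to a statistical or health-economic analysis plan, and one may exist.

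A reader might also infer that the planned comparison is biased. Under randomisation it is not, on average. Chance imbalance is sampling error, and the spread of the bootstrap already reflects it. What adjustment offers is a better estimate given the imbalance that occurred, and a narrower interval.

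A third tempting reading is that month-0 costs are summed into total costs. Section 10.2 lists when questionnaires are given, and section 8.3 describes the 3- to 12-month questionnaires as follow-up of the cost part. That fits a baseline value followed by outcome periods.

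Finally, every magnitude is assumed, and the direct share in step 2 is small against an SE of about 0.028.

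All of this stands and limits the claim. It does not remove the point that 10.2 names a method for the economic comparison, leaves that comparison outside the baseline-using methods of 10.1, and gives data already collected no stated role.

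**Conclusion.** The point holds as a nearly costless improvement and a request for clarity, not as the correction of an invalid analysis. Section 10.2 names no baseline adjustment for costs or utilities, although both baselines are collected. If QALYs are compared by the same mean-difference approach, the estimate is unbiased on average but carries chance imbalance and is less precise than the data allow.

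For a baseline-outcome correlation of 0.3 to 0.5 and about 69 completers per arm, adjustment lowers the SE by about 5 to 13%, as if there were about 76 to 92 patients per arm. At weaker correlations the gain is smaller; at 0.2 it is 2.0%. It cannot be shown what share of the incremental QALY an imbalance would make up, because the protocol states no expected incremental QALY. The point concerns a secondary objective and leaves the primary analysis untouched.

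**What to change.** In section 10.2:

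- Say how QALYs are formed from the EQ-5D.
- Estimate incremental QALYs and incremental costs by regression on approach (for example, seemingly unrelated regression), with baseline EQ-5D utility and month-0 costs as covariates, inside the same bootstrap that feeds the planes and acceptability curves.
- State that the month-0 costs are pre-operative, serve as a covariate and are not part of total costs.
- Keep the unadjusted comparison as a sensitivity analysis.

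If a separate analysis plan already specifies this, a cross-reference is enough. The choice should be fixed before the economic data are compared by arm, so that it does not depend on the imbalance observed. The cost is one or two sentences and slightly more analysis code; no new data are needed.
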